21.9 Safety Analyses

21.9.1 Adverse Events

The Medical Dictionary for Regulatory Activities (MedDRA) version 18.0 or later will be used to code all adverse events to a system organ class (SOC) and a preferred term (PT) within the SOC. The National Cancer Institute Common Terminology Criteria for Adverse Events (version 4.03; CTCAE) will be used to grade severity of all AEs.

The number and percentage of patients reporting each PT will be summarized by the treatment received in the period of onset. Incidence of AEs by maximum reported CTCAE grade will also be tabulated within each arm. The SAEs and AEs leading to study discontinuation will be displayed. The following summaries will be presented:

- Overall TEAEs
- Treatment-related TEAEs
- Adverse transfusion reactions
- TEAEs by maximum CTCAE grade
- SAEs and UADEs
- TEAEs causing discontinuation from the study
- All cause mortality
- Incidence of treatment-emergent antibody with confirmed specificity to RBCs derived from Mirasol-treated WB

Because all AEs will be recorded from the time of the first study related transfusion through the end of study treatment follow-up visit or early termination, any AEs will by definition be TEAEs. However, causation by treatment may not be determined for AEs observed at the final follow-up visit due to off protocol transfusions administered since last study transfusion.

21.9.2 Laboratory Tests

All laboratory values will be converted to International System of Units (SI units).

Laboratory test covered by the CTCAE (version 4.03) will be assigned grades accordingly. A grade of 0 will be assumed for non-missing values not graded as 1 or higher. In the unlikely cases where a laboratory normal range overlaps in the higher (ie, non-zero) CTCAE grade, the

laboratory value will still be taken as within normal limits and assigned a CTCAE grade of 0. Grade 5 will not be used.

For laboratory tests where grades are not defined by CTCAE, results will be graded by the low/normal/high classifications based on normal ranges.

The following summaries by treatment group will be presented separately for laboratory parameters: change from baseline to the time point prior to each transfusion and change from the pre transfusion time point between each consecutive transfusion.

22 STUDY MANAGEMENT

22.1 Investigator Responsibilities

22.1.1 Roles and responsibilities of Key Study Personnel

- Lead Investigator: overall responsibility over the trial
- Research Coordinator: procedures with the patients, maintain study records, enter data into database, contact with the Sponsor

This is a multicenter study and the delegation of authority log at each investigational site will further define the roles and responsibilities of study personnel.

22.1.2 Statement of Investigator

Each Investigator will provide to the Sponsor a current curriculum vitae and a signed Statement of Investigator prior to initiation of the study.

22.1.3 Institutional Review Board/Ethics Committee

The Institution's IRB/EC or other similarly functioning committee will review and approve the CIP, CIP amendments, initial/revised ICF documents, and recruitment materials, if applicable. Upon IRB/EC approval, documentation of that approval and the approved ICF documents will be sent to the Sponsor before any subject is enrolled into this study.

22.1.4 Informed Consent

The Investigator is responsible for preparing the written informed consent/parental consent/assent documents for this study. The Sponsor or designee will provide to the Investigator ICF/parental consent form/assent form templates. The Investigator may rearrange or reword the contents of the templates or may add other elements or language, provided the meaning and content are not changed or deleted. The site-specific ICF/parental consent form/assent form will be reviewed/approved by the Sponsor prior to submission to the IRB/EC.

Written informed consent/parental consent/assent will be obtained from all subjects/legal guardians participating in this study. The case history for each subject must document that the informed consent/parental consent/assent process was conducted prior to participation in the study. The original ICF/parental consent form/assent form will be kept in the subject's record, and a copy will be provided to the patient.

All subjects are free to withdraw from participation in this study at any time, for any reasons, specified or unspecified, and without prejudice. The reason for the patient discontinuing or terminating from the study must be recorded on the eCRF.

22.1.5 Record Retention

Investigational sites will maintain all records pertaining to this study for the longer of the following time periods:

- A minimum of 2 years following premarket approval (or applicable application); OR
- 2 years after the study was discontinued

Thirty (30) days before destroying any study-related records, investigational sites will provide written notice to the Sponsor.

Investigators must notify the Sponsor in the event they are leaving the institution.

22.2 Recording and Collecting of Data

The Investigator will maintain complete, accurate, legible, and easily retrievable data. The Investigator will provide access for Sponsor authorized personnel to all study data at any time. Such data shall also be secured in order to prevent loss of data.

All required data for this study will be recorded from the source documentation onto standardized eCRFs.

For the duration of the study, the Investigator will maintain complete and accurate documentation, including but not limited to, medical records, study progress notes, laboratory reports, signed patient informed consent forms, device accountability logs, correspondence with the reviewing IRB/EC, sponsor and study monitor, adverse event reports, and information regarding patient discontinuation or completion of the study.

The Investigator/institution will permit direct access to source data and documents in order for study-related monitoring, audits, IRB/EC reviews, event adjudication and regulatory inspections to be performed. The Investigator will obtain, as part of the informed consent process, permission for sponsor, authorized sponsor employees or representatives, representatives of the United States Army Medical Research and Materiel Command, study monitors or regulatory authorities to review, in confidence, records that identify patients in this trial.

Accurate and complete study records will be maintained and made available to representatives of the United States Army Medical Research and Materiel Command. These representatives are authorized to review research records as part of their responsibility to protect human research volunteers. Research records will be stored in a confidential manner so as to protect the confidentiality of patient information.

22.2.1 Source Documents

Source data is all information, original records of clinical findings, observations, or other activities in a clinical trial necessary for the reconstruction and evaluation of that trial. Source data are contained in source documents. Examples of these original documents and data records include hospital and clinic records, evaluation checklists, scan or laboratory results, etc.

22.2.2 Case Report Forms

The study CRF via EDC is the primary data collection instrument for the study. All data must be recorded in English. Any missing data must be explained.

Completed CRFs will be reviewed and signed by the Investigator. The CRA will verify the EDC data with the patient's source data, evaluate the data for accuracy, consistency, and completeness, and will ensure that all forms with missing data and/or errors are ultimately addressed. Accurate and complete CRFs for a patient must be completed in a timely manner.

22.3 Clinical Investigation Plan Compliance

The Investigator is responsible for ensuring the study is conducted in accordance with the procedures and evaluations described in this CIP.

22.3.1 Deviations from the Clinical Investigation Plan

A CIP deviation is defined as any event where the investigator or site personnel deviate from the study CIP or study procedures for any reason.

It is the Investigator's responsibility to ensure that there are no CIP deviations throughout the lifetime of the study and that the study is conducted in full compliance with the CIP and all established procedures and conditions of the reviewing IRB/EC. CIP deviations that are due to unforeseen circumstances beyond the Investigator's reference, (eg, if the patient did not arrive for their scheduled follow-up and had to be re-scheduled outside of the CIP-defined time-window) are required to be reported on the CIP deviation form in order to ensure that all deviations from the standard subject population are adequately documented and reported.

The Investigator will inform the sponsor of all deviations and will inform the reviewing IRB/EC of CIP deviations per IRB/EC requirements. The occurrence of CIP deviations will be monitored

by the Sponsor for evaluation of Investigator compliance to the CIP, GCP compliance, and regulatory requirements. The Sponsor will report all deviations that are considered a modification to the CIP, pose a risk to the patient or that affect the scientific integrity of the study to HRPO. In the event that an Investigator does not comply with the clinical study/Investigator agreement, and/or the CIP, the Investigator will be notified of their noncompliance, and the Sponsor will review the circumstances. Continued noncompliance may result in discontinued shipment of study devices and termination of the Investigator's and/or investigational site's participation in the study.

The Investigator will not deviate from the CIP for any reason without prior written approval from the sponsor, except in cases of medical emergencies. A medical emergency is defined as a medical condition where no other medical option exists for satisfactory survival of the patient. In the case of a medical emergency, the Investigator should notify the sponsor as soon as possible, in writing, of the emergency use of the device.

22.4 Sponsor Responsibilities

22.4.1 Amendments to the Clinical Investigation Plan

Any amendment to the CIP, as deemed appropriate by the Sponsor, will be implemented as the study progresses. Amendments will be submitted to the IRB/EC for written approval before implementation.

22.4.2 General Responsibilities of Sponsors

As per ISO 14155 Section 8 and 21 CFR 812, the Sponsor is responsible for selecting qualified Investigators and providing them with the information they need to conduct the investigation properly, ensuring quality study conduct and proper monitoring of the investigation, ensuring required approvals are obtained and that significant new information about an investigation is promptly reported to reviewing IRB/EC and government authorities as well as annual reports as required. Sponsor or designee will maintain essential study documentation.

22.4.3 USAMRMC Review, Approval, and Continuing Review

The study will be conducted in accordance with the CIP submitted to and approved by the ORP HRPO and will not be initiated until written notification of approval of the research project is issued by the ORP HRPO.

A copy of the continuing review report for the research study will be submitted to the local IRB/EC. A copy of the approved continuing review report and the local IRB/EC approval notification must be submitted to the ORP HRPO as soon as these documents become available. In addition to reporting progress of the approved research to the local IRB/EC, as described

above, the sponsor will provide progress reports to the ORP HRPO as often as requested, but not less frequently than once per year.

22.5 Joint Investigator/Sponsor Responsibilities

22.5.1 Training

The Sponsor will train applicable study team members to the device, CIP, and study procedures and will provide updated information as it becomes available during the course of the study, if applicable. The Investigator is responsible for ensuring that additional site personnel that were not trained by the Sponsor receive applicable documents and training.

22.5.2 Compliance

The study will be conducted in accordance with the ethical principles that have their origin in the Declaration of Helsinki, United States CFR, ISO14155/2011 and any regional or national regulations, as appropriate. The study will not begin until the required approvals/favorable opinion from the local IRB/EC and the regulatory authority have been obtained.

22.5.3 On Site Audits

In accordance with the Sponsor's operating procedures, the Sponsor or designee may request access to all study records, including source documents, for inspection and duplication. In the event that an Investigator is contacted by a regulatory agency in relation to this study, the Investigator will notify the Sponsor immediately.

The Investigator or designee must be available to respond to reasonable requests and audit queries made by authorized regulatory representatives during the audit process. The Investigator must provide the Sponsor with copies of all correspondence that may affect the review of the current study or their qualification as an Investigator in clinical studies conducted by the Sponsor. The Sponsor will provide any needed assistance to regulatory audits or correspondence.

Accurate and complete study records will be maintained and made available to representatives of the USAMRMC. These representatives are authorized to review research records as part of their responsibility to protect human research volunteers. Research records will be stored in a confidential manner so as to protect the confidentiality of patient information.

The knowledge of any pending compliance inspection/visit by the FDA, Office of Human Research Protections, or any other government agency concerning this clinical investigation or research, the issuance of Inspection Reports, FDA Form 483, warning letters, or actions taken by any regulatory agencies including legal or medical actions and any instances of serious or continuing non-compliance with the regulations or requirements will be reported immediately to USAMRMC ORP HRPO.

22.5.4 Termination of the Study

For reasonable cause, either the Investigator or the Sponsor may terminate the Investigator's participation in this study, provided a written notice is submitted within the time period provided for in the Clinical Trial Agreement (CTA). In addition, the Sponsor may terminate the study at any time upon immediate notice for any reason, including but not limited to, the Sponsor's belief that termination is necessary for the safety of patients.

The ORP HRPO will be notified upon completion of the study. A copy of the final study report will be submitted to the local IRB/EC. A copy of the approved/accepted final study report and the local IRB/EC approval/acceptance notification must be submitted to the ORP HRPO as soon as these documents become available.

22.5.5 Financing

The Sponsor will compensate the Investigator Sites according to the terms of a CTA between the Sponsor, the Investigator, and the Investigator Site that will list the anticipated cost and expenses relating to the conduct of this study. However, the Sponsor will not compensate the Investigator for evaluation of patients in a manner other than specified in the CIP.

The Investigator is not financially attached to private enterprises, foundations, etc., that may have interests in this clinical study.

22.5.6 Publication Policy

The Sponsor recognizes the importance of communication of medical study data. The Sponsor encourages the publication of such data in reputable scientific journals and the presentation of such data at scientific seminars and conferences. Any proposed publication or presentation of the data generated from the study must be provided to the Sponsor for timely review in accordance with the terms of the CTA between the Investigator, the Institution, and the Sponsor. The Sponsor shall not, in its scientific publications or promotional material, quote from publications by Investigators without full acknowledgment of the source. Because this will be a multisite trial, all Investigators agree not to publish individual site data without prior approval from the Sponsor, as negotiated in the CTA. All trial data will be published as 1 or more manuscripts based on the accumulated data from all trial sites.

## **I. Introduction**

### **A. Background**

Thalassemia is a congenital blood disorder, categorized as either alpha-thalassemia or beta thalassemia, in which production of alpha or beta globin is decreased or absent, respectively resulting in lack of hemoglobin (Hb) production. Thalassemia major (homozygous) is the most severe form of the disease, requiring red blood cell (RBC) transfusions from an early age.

The current standard of care for transfusion-dependent thalassemia patients dictates chronic RBC transfusions with the goal of controlling anemia and suppressing ineffective erythropoiesis. Treatment with chronic RBC transfusions requires that these thalassemia patients are exposed to multiple blood products from multiple donors, increasing the risk of transfusion transmitted infections (TTI) by unscreened or undetected pathogens in the blood supply and transfusion-related immune reactions. In Vinchinsky et al., 24% of transfused thalassemia patients had laboratory evidence of previous exposure to one or more infectious diseases. Mirasol-treated blood products resulting in pathogen reduction and white blood cell (WBC) inactivation may provide a safer primary treatment for this population.

This study will provide valuable information about Mirasol-treated blood products regarding blood safety.

### **B. Protocol and Amendment History**

This Statistical Analysis Plan (SAP) is based on version 4.1 /28AUG2017 of Protocol CTS-5056, which will incorporate Amendment x.

This SAP will govern the analysis of data from this study. Any modifications to the SAP will be done by a blinded statistician without access to the study data prior to database lock. Any deviations from the SAP, including any after database lock, will be documented as such in the clinical study report.

## **II. Protocol Objectives**

### **A. Primary**

- To determine if percent survival of RBCs derived from Mirasol-treated whole blood (WB) is non-inferior to conventional RBCs when transfused into patients requiring chronic RBC transfusion support.

### **B. Secondary**

- To compare other efficacy and safety endpoints between treatment groups

## **III. Study Endpoints**

### **A. Efficacy Endpoint**

#### **1. Primary**

- Normalized hemoglobin area under the curve (Hb AUC) calculated from normalized Hb between successive transfusions as a measure of percent surviving RBCs

#### **2. Secondary**

- Hb increment
- Actual Hb level post-transfusion (15min)
- Proportional decline in post-transfusion Hb level
- RBC mass infused (volume x Hb/unit)

### **B. Safety Endpoints**

- Incidence of treatment-emergent antibody with confirmed specificity to RBCs derived from Mirasol-treated WB
- Human leukocyte antigen (HLA) alloimmunization rates
- Treatment emergent adverse events (TEAEs)
- Transfusion-related adverse events (AEs)
- Serious adverse events (SAEs)
- Unanticipated adverse device effects (UADEs)

## IV. Study Design

### A. Design Overview

This is a prospective, multi-center, randomized, crossover trial to evaluate the clinical effectiveness of RBCs derived from Mirasol-treated WB (MIR RBCs) versus conventional RBCs (REF RBCs) in transfusion dependent thalassemia patients. Throughout the clinical trial, RBC transfusion volume and frequency will be determined by each subject's treating physician.

Eligible subjects who have signed an informed consent form (ICF)/parental consent form and assent form, where applicable, will be enrolled and randomized 1:1 to a treatment sequence via an electronic system using a permuted-block schedule stratified by investigational site. Subjects will be randomized to receive either MIR RBCs followed by REF RBCs, or to receive REF RBCs followed by MIR RBCs.

The crossover trial design will consist of 2 treatment periods. Each period will include a 50-day wash-in phase (Day 0 of the wash-in = Day 0 of the treatment period) followed by 2 transfusion episodes for assessment of the primary endpoint. The 50-day wash-in serves to ensure that an adequate volume of RBCs from the assigned treatment allocation (MIR RBCs versus REF RBCs) have been transfused into the subject prior to collecting samples to support the primary endpoint.

An end of study treatment follow-up visit will occur 2-4 weeks after the last per protocol transfusion, which should coincide with the next standard of care transfusion. A final study visit will occur at least 60 days after the last per protocol transfusion.

During each treatment period, blood samples will be collected for safety and efficacy analysis.

Blinding is not feasible because riboflavin used in the Mirasol-treated WB may cause yellow colored urine in transfusion recipients of Mirasol-treated blood products. Also, there is a difference in MIR RBC and REF RBC storage bags and labels. However, subjects, investigational site staff, and the Sponsor will not be informed of the randomization assignment. Study team members conducting safety assessments on subjects should remain blinded, whenever possible, to ensure causality determination remains unbiased. Central and Local Blood Centers will be informed of the randomization assignment to provide study product for transfusion.

## B. Study Population

The study population will consist of transfusion-dependent thalassemia patients. 97 patients will be randomized at up to 10 transfusion centers and corresponding blood centers with sites in the United States and outside of the United States (e.g., Europe, Canada, or the Middle East).

## C. Sample Size Estimation

Data from the IMPROVE II study were available to obtain information on normalized Hb AUC associated with RBCs derived from Mirasol-treated WB as well as from untreated WB. Pairwise differences in the natural log-transform of normalized Hb AUC from treatment and control were used to obtain estimates required for determining the sample size needed for this study.

The mean difference in log-transformed Hb AUC values suggests a reduction of 16.7% resulting from the use of MIR RBCs. The sample variance of within subject differences is 0.015412. The estimate of the within subject variance required for the 2x2 crossover design is one-half of the variance of within subject differences (0.007706).

The primary hypothesis is that RBCs derived from Mirasol-treated WB are not inferior to conventional, untreated RBCs with respect to normalized Hb AUC. Assuming a within subject variance of 0.007706 and a 16.7% reduction in normalized Hb AUC, approximately 77 subjects are needed to obtain at least 80% power to show the decrease in normalized Hb AUC from RBCs derived from Mirasol-treated WB is not more than 20% of the normalized Hb AUC from conventional untreated RBCs assuming a 1 tailed type 1 error rate of 2.5%. Algebraically if  $\ln(\mu_M)$  is the mean of the natural log-transformed Hb AUC for MIR RBCs and  $\ln(\mu_C)$  is the mean of the natural log-transformed Hb AUC for REF RBCs, the sample size is calculated to detect an alternative hypothesis versus a null hypothesis stated as:

$$H_0 : \ln(\mu_M) - \ln(\mu_C) \leq -22.3\% \text{ versus } H_a : \ln(\mu_M) - \ln(\mu_C) > -22.3\%$$

In the original scale (indicated by \*), the above hypotheses translate to:

$$H_0 : \frac{\mu_M^*}{\mu_C^*} \leq 0.80 \text{ versus } H_a : \frac{\mu_M^*}{\mu_C^*} > 0.80$$

Assuming a potential 20% discontinuation rate, approximately 97 patients may be enrolled.

The sample size was calculated using SAS 9.3 proc power for paired two samples t-test with option for finding difference with the null difference at the non-inferiority margin of -0.2231 (corresponding to 20% non-inferiority margin at the original scale), true mean of -0.1839 (corresponding to 16.7% observed

decrease in IMPROVE II), and correlation of 0.35. Should the correlation be higher, the proposed sample size will have higher power for the non-inferiority test.

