21.8 Sample Size Rationale

Data from the IMPROVE II study were available to obtain information on normalized Hb AUC associated with RBCs derived from Mirasol-treated WB as well as from untreated WB. Pairwise differences in the natural log-transform of normalized Hb AUC from treatment and control were used to obtain estimates required for determining the sample size needed for this study.

The mean difference in log-transformed Hb AUC values suggests a reduction of 16.7% resulting from the use of RBCs derived from Mirasol-treated WB. The sample variance of within subject differences is 0.015412. The estimate of the within subject variance required for the 2x2 crossover design is one-half of the variance of within subject differences (0.007706).

The primary hypothesis is that RBCs derived from Mirasol-treated WB are not inferior to conventional, untreated RBCs with respect to Hb AUC. Assuming a within subject variance of 0.007706 and a 16.7% reduction in Hb AUC, approximately 77 subjects are needed to obtain at least 80% power to show the decrease in Hb AUC from RBCs derived from Mirasol-treated WB is not more than 20% of the Hb AUC less from conventional untreated RBCs assuming a 1 tailed type 1 error rate of 2.5%. Algebraically if $\ln(\mu_M)$ is the mean of the natural log-transformed Hb AUC for RBCs derived from Mirasol-treated WB and $\ln(\mu_C)$ is the mean of the natural log-transformed Hb AUC for conventional untreated RBCs, the sample size is calculated to detect an alternative hypothesis versus a null hypothesis stated as:

$$H_0 : \ln(\mu_M) - \ln(\mu_C) \leq -22.3\% \text{ versus } H_a : \ln(\mu_M) - \ln(\mu_C) > -22.3\%$$

In the original scale (indicated by *), the above hypotheses translate to:

$$H_0 : \frac{\mu_M^*}{\mu_C^*} \leq 0.80 \text{ versus } H_a : \frac{\mu_M^*}{\mu_C^*} > 0.80$$

Assuming a potential 20% discontinuation rate, approximately 97 patients may be enrolled.

The sample size was calculated using SAS 9.3 proc power for paired two samples t-test with option for finding difference with the null difference at the non-inferiority margin of -0.2231 (corresponding to 20% non-inferiority margin at the original scale), true mean of -0.1839

(corresponding to 16.7% observed decrease in IMPROVE II), and correlation of 0.35. Should the correlation be higher, the proposed sample size will have higher power for the non-inferiority test.

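### The log-scale true mean of -0.1839 printed for the sample-size run is not the log of a 16.7% reduction, and the stated 77 subjects and 80% power reproduce from 16.7% but not from -0.1839

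*SAP*

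**What the plan says.** SAP IV.C and Protocol 21.8 give the same sizing argument. From IMPROVE II they take a 16.7% reduction and a difference variance: "The sample variance of within subject differences is 0.015412". Half of that is used as the within-subject variance ("one-half of the variance of within subject differences (0.007706"). The sizing statement begins "Assuming a within subject variance of 0.007706 and a 16.7% reduction in normalized Hb AUC" and concludes that "approximately 77 subjects are needed to obtain at least 80% power", "assuming a 1 tailed type 1 error rate of 2.5"%. A 20% discontinuation rate then raises 77 to 97 enrolled.

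A closing paragraph describes the software run: PROC POWER, paired t-test, null difference -0.2231 (20% margin) and a "true mean of -0.1839 (corresponding to 16.7% observed" decrease in IMPROVE II, with a "correlation of 0.35". The protocol's version reads "corresponding to 16.7% observed decrease in IMPROVE II), and correlation of 0.35". Neither document prints the marginal SD that would be entered with that correlation.

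The 16.7% figure also appears in Protocol 19.3.3, and Protocol 5.2 gives the treated AUC as about 83% of control. The protocol synopsis describes the power as approximately 80%. It gives neither -0.1839 nor 16.7%.

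**The concern.** The closing paragraph presents -0.1839 and 16.7% as the same quantity on two scales, and they are not. Rounding does not explain the gap. Every reduction that rounds to 16.7% (16.65% to 16.75%) has a log between -0.1821 and -0.1833, and -0.1839 lies outside that range. The margin in the same sentence is converted correctly to four decimals (ln 0.80 = -0.2231), so the reader expects the same accuracy for the true mean.

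The difference matters only because the assumed effect lies about 0.04 log units from the margin. A shift of 0.0012 in the true mean is about 3% of that distance, which is enough to move power at 77 across the 80% line. Anyone checking the sizing from the printed software inputs would not recover the printed result. The SAP plans no sample-size reassessment, so no later step would reconcile the figures.

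**Working it through.** **Inputs** (SAP IV.C; the same values are in Protocol 21.8)

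- One-sided alpha 0.025; target power at least 80%; stated N = 77.
- Variance of within-subject differences 0.015412, so SD = √0.015412 = 0.1241.
- Null difference -0.2231.
- True mean: either 16.7% on the original scale or -0.1839 on the log scale.

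**Conversion**

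- 1 − exp(-0.1839) = 0.1680, a 16.8% reduction.
- ln(1 − 0.167) = ln(0.833) = -0.1827.

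**Power formula.** Paired t-test on log differences, with n − 1 degrees of freedom and noncentrality (true mean − null) / (SD/√n). Power is the probability that the noncentral t exceeds the 97.5% point of the central t. At n = 77 the standard error is 0.1241/√77 = 0.01415 and the critical value is 1.992.

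**The plan's own figure, from 16.7%**

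- Distance: -0.1827 + 0.2231 = 0.0404.
- Noncentrality: 0.0404/0.01415 = 2.85.
- Power at 77 = 80.5%; the smallest n for 80% is 77.
- 77/0.8 = 96.25, rounded up to 97.

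This reproduces the stated 77, the stated power and the stated 97.

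**The printed log-scale input, -0.1839**

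- Distance: -0.1839 + 0.2231 = 0.0392.
- Noncentrality: 0.0392/0.01415 = 2.77.
- Power at 77 = 78.1%; the smallest n for 80% is 81 (80.2%).
- 81/0.8 = 101.25, rounded up to 102.

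| True mean | Reduction | Power at 77 | N for 80% | After 20% dropout |
|---|---|---|---|---|
| -0.1827 | 16.7% | 80.5% | 77 | 97 |
| -0.1839 | 16.8% | 78.1% | 81 | 102 |

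**Variants with -0.1839 and the printed variance**

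- Normal approximation: N = 79, power at 77 = 79.1%.
- n − 2 degrees of freedom: N = 81.
- Unrounded ln(0.80) as the null: N = 81, power at 77 = 78.2%.

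None returns 77 with 80% power.

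**The correlation of 0.35.** In this parameterization the difference variance is 2 × SD² × (1 − 0.35).

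- A marginal SD of 0.1089 returns the printed 0.015412, so the results above stand.
- If 0.007706 had been entered as the marginal variance, the difference variance would be 2 × 0.007706 × 0.65 = 0.01002 and N would be 54 with -0.1839.
- Assumed for illustration, not in the documents: a marginal SD of 0.106 gives 2 × 0.106² × 0.65 = 0.01461. With -0.1839 that yields N = 77 and 80.2% power. The stated N could therefore come from -0.1839 with a different SD, but that SD would contradict the printed variance.

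**The case against.** The strongest objection is that the sizing claim itself is sound. The documents say that 77 subjects suffice for a 16.7% reduction with a within-subject variance of 0.007706, and that reproduces exactly. The 16.7% is repeated elsewhere in the protocol, and only the parenthetical -0.1839 is out of line. A misprint or a slip in the transformation is therefore the likelier explanation. This stands, and it rules out the stronger reading that a reader might take from the 78.1%, namely that the trial is too small or that its power statement is false.

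Second, the actual run cannot be reconstructed, because the SD entered with the correlation of 0.35 is not printed. This also stands. The error could lie in the true mean, in the stated power or in the SD. It does not remove the inconsistency, because no choice of SD makes -0.1839 equal to 16.7%.

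Third, the effect is small. The power shortfall is 80 − 78.1 = 1.9 points, against sample sizes that the plan itself calls approximate. Rounding of the 16.7% alone moves N between 74 (at 16.65%) and 79 (at 16.75%). The variance comes from the 24 evaluable healthy volunteers of IMPROVE II, and that uncertainty is probably larger. This limits the weight of the point but does not excuse an input that contradicts its own description.

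A reader might also suppose that the protocol and SAP disagree with each other, or that the synopsis is wrong. Neither is so. Both documents print the same values, so the mismatch lies within each section, and the synopsis says only approximately 80%.

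**Conclusion.** The inconsistency is certain: -0.1839 is a 16.8% reduction, and a 16.7% reduction is -0.1827. With the printed difference variance and the stated paired t-test, the plan's 77 subjects and minimum power follow from -0.1827 (80.5%) and not from -0.1839 (78.1% at 77; 81 for 80%).

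The documents do not support the conclusion that 77 is wrong or that the trial is underpowered. The 78.1% and N = 81 hold only if -0.1839 and the variance of 0.015412 were both the values actually used, and the documents cannot settle that. The margin, the test and the decision rule are unaffected. The point deserves correction because a sizing input and the stated power should agree, and at present they do not.

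**What to change.** Check the archived PROC POWER program and output, including the SD entered with the correlation of 0.35. Then make the percentage, log mean, variance and power agree within both Protocol 21.8 and SAP IV.C:

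- If 16.7% was the input, change -0.1839 to -0.1827 and leave 77 and the power statement as they are.
- If -0.1839 was the input with the printed variance, state a 16.8% reduction and replace the 80% minimum with about 78% power at 77.
- If a different SD was entered, correct the printed variance or restate the power to match it, and state the percentage that belongs to the log mean used.

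It would also help to print the IMPROVE II mean log difference to four decimals and the SD used. The synopsis needs no change if -0.1827 is right. If the restated power is about 78%, check whether its approximate wording should remain.

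The cost is wording in two sections. No extra patients are needed, though the stated power may become slightly less favourable.
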